### **The pilot study aims are to:**

1. Develop our proposed preliminary computer-based intervention, incorporating information gained in focus groups.
2. Perform a small open trial (N = 15) of SHE to assess feasibility of recruitment of target population and acceptability of intervention and study procedures.
3. Conduct a randomized pilot trial in a sample of 60 battered sheltered women who report substance use problems within the three months prior to entering the shelter, to demonstrate the feasibility of SHE and the acceptability of SHE via participant report of ease of use, helpfulness, and overall satisfaction.
4. Examine preliminary evidence that relative to control condition, the computer-based intervention (SHE) will result in improvements in our primary outcomes of substance use (heavy drinking or drug using) days over a 6-month post-shelter period and in our secondary outcomes of greater use of substance use services (both treatment and self-help utilization) and reduced IPV severity over a 6-month post-shelter period. Theorized

mediators include readiness to change and self-efficacy for behaviors related to substance use.

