
be assessed with the Woman Abuse Screening Tool (WAST). The WAST is an 8-item instrument that measures physical, sexual, and emotional abuse and is consistent with the definition of IPV as defined by The American College of Obstetricians and Gynecologists. It has correctly classified 100% of nonabused women and 92% of abused women in a known-group analysis, has good internal reliability, and has adequate concurrent validity, even with ethnic minorities. Consistent with similar studies, IPV status will be positive if a woman obtains a score of 4 or more on the WAST.

All participants screened will receive a standard health information brochure with further information and resources on the health topics mentioned, including a list of local substance use treatment referrals and community resources. Those meeting full inclusion criteria will be asked to provide signed informed consent and complete the computer based baseline assessments. All participants will be advised to keep their copy of the consent form in a secure location, or to discard this form if it is unsafe for them to keep it.

**Inclusion criteria:** Women who are 18 or older, residents of a battered women’s shelter (the Women’s Center of Rhode Island [WCRI], Sojourner House, New Hope, or Battered Women’s Shelter of Summit and Medina Counties), who are at risk substance users within the 3 months prior to entering the shelter, as determined by the screener, the NIDA-Modified ASSIST, and endorse IPV within the 3 months prior to entering the shelter, as determined by the screener, the WAST

**Exclusion criteria:** includes: 1) inability to provide informed consent (e.g., due to florid psychosis or other, clear cognitive impairment), 2) inability to understand English (understand the consent form when read aloud. 3) No endorsement on the baseline TLFB for substance use and/or intimate partner violence in the 3 months prior to shelter stay.

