## Measures

Participants who screen positive for substance use problems and IPV within the 3 months prior to shelter stay during screening will complete an approximately 20-30 minute baseline assessment session on the Tablet PC. Screening measures for at risk substance use and IPV are the same as the open trial and include the NIDA-Modified ASSIST and the WAST, respectively. Most measures for this study will be completed by participants using the Audio Computer-based Assisted Self-Interview (ACASI) software and the Tablet PC. If there are any technical issues with the Tablet PC, paper copies of the same measures will be offered to participants to complete. Like the data completed on the tablet, the paper versions of the measures will be de-identified data. Measures will be administered to both groups of women at baseline (i.e., after screening and consent) and at 3- and 6 months after shelter discharge. The baseline battery is designed to minimize assessment with the control group in order to take into account growing concerns regarding the motivational properties of assessment, leading to substantial Type II error in other MI-based intervention studies.

**Demographic measures:** All participants will complete demographic information, including age, race, ethnicity, educational level, marital status, occupation, employment (status, # hours per week), socioeconomic status, etc. See Table 1 for the time schedule for the study assessments.

**Acceptability:** *Satisfaction with CIAS Software Scale (SSS)* assesses participant satisfaction on items tapping on likeability, ease of use, level of interest, and respectfulness. Participants will also complete the well-studied 8-item *Client Satisfaction Questionnaire-Revised (CSQ-8-R)* to assess satisfaction with the intervention. These scales will be administered after each computer-based session (i.e., initial session and booster session) and administered to both conditions.

The following measures will be administered to both groups of women at baseline and at 3- and 6- months after leaving the shelter.

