**Primary outcome measures:** *Alcohol and Substance use: Timeline Follow-Back (TLFB)-modified computer version* has yielded comparable results to face-to-face interview administrations. The computer-based TLFB will assess drug use and heavy drinking (4+ standard drinks) days for the past week and the past 90 days from entering in the shelter. The TLFB will be done in person as well. For primary analysis, days using drugs and heavy drinking days will be combined to create a single variable that reflects the total number of days that women used drugs or had 4+ drinks. The TLFB has excellent reliability, and is sensitive to change as used in this study. (We will not collect collateral (i.e., from a significant other) reports of subjects' use to corroborate yes/no use of substances because this could pose a risk to confidentiality for the participant, who might be particularly vulnerable if she is experiencing IPV). To provide objective corroboration of self-reported drug use, *hair sample testing* (Psychemedics, Inc) at the 3- and 6-month will be obtained to give an approximately 90-day window of evidence for cocaine, marijuana, amphetamine, or opiate use.

We will report correlations between self-report and biological measures of substance use. *Breath alcohol tests* will be conducted at each follow-up assessment (i.e., at the 3 months and 6 months periods in order to insure that the client has consumed no alcohol prior to the assessment (breath alcohol content < .02). If the participant has been consuming alcohol, the assessment will be rescheduled. Urine drug screen results will also be reviewed to corroborate

self-report data at the 3- and 6- month assessments. Urine drug screens will use the CLIA waived, Inc. Instant Drug Test Cup-7 Panel Cup (ICTC), be unobserved, and test for benzodiazepines, cocaine, methamphetamine, methadone, opioids, oxycodone, and THC. .

Secondary Outcomes: *The Treatment Services Review (TSR)* will be used to assess total days of substance use services (both treatment and self-help utilization) received (including outpatient, day patient, residential treatment, NA, AA) to capture the extent to which women are reaching out to access recovery-related resources. At baseline and at each follow-up point, the TSR will assess total days of substance use services received for a 90 day window.

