IPV: The Composite Abuse Scale (CAS) is a widely used self-report of behaviors scale with 4 subscales that measure severe, combined abuse, emotional abuse, physical abuse, and harassment. The CAS has recently been published in the Centers for Disease Control and Prevention compendium of intimate partner violence measures. It consists of 30 items presented in a six point format requiring respondents to answer “never”, “only once”, “several times”, “monthly”, “weekly” or “daily” in a twelve month period.

The Cyber Stalking Scale measure is a 6 –item measure and assesses the use of technologies in stalking and harassment.

Safety Behavior Checklist (SBC) has 15 items that assess the use of strategies suggested to keep victim safe (e.g., hiding money and extra clothing).

*Theorized Mediators: The Confidence Ladder* will be used to assess the participants’ levels of confidence regarding their ability (self-efficacy) to change and abstain from substances. *Readiness Ruler* will be used to assess the degree to which participants’ are ready to cut down or quit alcohol or drugs.

Women who participated in the SHE intervention will complete a computer-based measure at the 3- and 6-month follow-up assessment to determine the extent to which participants achieved their goals on their personalized plan; an indication of the degree to which the SHE intervention had an impact on behavioral change. This measure will follow a similar format to the Effectiveness in Obtaining Resources Scale, which assesses battered women’s effectiveness in obtaining various resources.

At follow up, if a participant is unable to meet in-person to complete the assessments (e.g. participant has moved out of state), she will be given the option of participating in the assessment over the phone. Phone sessions will consist of the research assistant administering all the follow up assessments listed above via a phone session, with the exception of breathalyzer, urine, and hair sample testing.

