Details of the research are not provided to anyone other than the actual participant. During each contact, participants will first be asked if it is a safe time to speak. Safe contact for follow-up assessments will be negotiated at each stage of the research. Both written and verbal contacts will be vague and never mention that the research involves partner violence. Follow-up interviews will be scheduled at a safe location. Safety plans will be negotiated up front (e.g., code words, cover story for reason for interview) if ever the abuser were to interrupt a phone call or assessment. Any handouts with important information (e.g., hotline numbers) will be available in wallet size copies without any reference to the study or name of organization. Participants' safety contact information will be updated monthly to determine if the contact information they previously provided is still accurate and safe. Participants will be given contact information for the research team and asked to let us know if the contact information they provided is no longer safe. All research personnel (i.e., interventionist, research assistant) will be able to call the PI for advice on any case where there is a concern for the safety of the respondent and the PI will be available at all times by pager.

Although the proposed intervention seeks to help a woman to develop strategies for keeping herself safe, it is possible that a woman who participates in the study might be at increased risk of partner violence because of increased assertiveness. At each follow-up assessment, our assessment of community resource use will ask about participants' visits to emergency rooms, health professionals, etc. The Composite Abuse Scale (CAS) will be administered to monitor abusive experiences in the context of a woman's relationship since the last assessment. Women will be asked at follow up assessments (3- and 6-month) about any occurrences of hospitalizations for medical, psychiatric, or substance use issues or emergency room visits, and whether or not any of these events were related to IPV in order to better gather information regarding any potential serious adverse events. These events will be reported to the Data Safety Monitoring Board (DSMB).

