### **Data Analysis:**

For this treatment development grant, assessment of feasibility and acceptability of the intervention and research procedures is the primary goal. Nonetheless, pilot data can be used to demonstrate whether the effects of treatment look promising across a set of outcome variables, to begin to examine distribution of outcome variables and ranges of correlations among variables across time to inform future analytic strategies, and to suggest, in concert with results from larger scale clinical trials in related fields, the range of effect sizes that would be reasonable to expect in a future trial. As a result, we will obtain the between treatment condition effect size estimates at each assessment (e.g., Cohen's *d* or *h*) as well as the correlation between the same dependent variable at adjacent assessments. We anticipate we will have complete data on approximately 41 participants. Sample size guidelines for treatment development from Rounsaville et al. recommend 15 to 30 participants per cell. Given that group means begin to stabilize by around 15, we believe a sample of ~20-21 in each condition should provide some information relevant to demonstrating potential promise for the intervention.

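### The recall period of the Composite Abuse Scale is not reconciled within the Protocol, so the look-back behind the IPV severity score and its planned pre-post change is unsettled

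*Protocol*

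**What the plan says.** Aim 4 of the Protocol names as a secondary outcome "reduced IPV severity over a 6-month post-shelter period". The SAP overview repeats this aim but does not name the CAS or give any recall period.

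The Protocol's Measures section introduces its outcome instruments with "The following measures will be administered to both groups of women at baseline and at 3- and 6- months after leaving the shelter". The CAS paragraph that follows describes 30 items with six frequency options, answered "in a twelve month period", and cites the published scale. Table 1 schedules the CAS at intake and at 3 and 6 months after discharge.

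Under Protection against risk, the CAS is to monitor abuse in the woman's "relationship since the last assessment".

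The Data Analysis section defines IPV severity as the count of abusive acts endorsed on the CAS, with no look-back. It plans a pre-post change in the intervention arm, between-arm effect sizes with 95% confidence intervals, and exploratory hierarchical linear models with the baseline score as covariate. For planning the next trial it will also report "the correlation between the same dependent variable at adjacent assessments".

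The other outcomes are more definite. For service use, "the TSR will assess total days of substance use services received for a 90 day window", at baseline and each follow-up. The Timeline Follow-Back (TLFB) uses 90 days tied to shelter entry. Eligibility requires that women "endorse IPV within the 3 months prior to entering the shelter".

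**The concern.** A count of acts endorsed depends directly on how far back the woman is asked to look. An act that happened once before shelter entry stays endorsed for as long as the window reaches back to it, even if all abuse has stopped. The Protocol gives two look-backs for the same instrument, and the section that turns answers into an outcome chooses neither.

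Three planned results are exposed: the between-arm effect size, the pre-post change in the intervention arm, and the correlation between adjacent visits. The Protocol intends its results as preliminary data for a fully powered trial, so a window artefact could carry into that trial's planning. No feasibility or acceptability result depends on it.

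**Working it through.** **Step 1. The places side by side**

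| Place | Look-back for the CAS |
|---|---|
| Protocol, Measures | twelve months (partly a description of the published scale) |
| Protocol, Protection against risk | since the last assessment |
| Protocol, Data Analysis | none stated |
| SAP | CAS not named |

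Since-last-assessment has no meaning at baseline, where there is no earlier CAS. At the 3-month visit it covers 3 months plus any stay remaining after baseline. At the 6-month visit it covers 3 months.

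**Step 2. Reading A: twelve months at every visit**

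Let t be the visit (3 or 6 months after discharge) and s the shelter stay in months. The documents do not give s; I assume 0.5 to 2.

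- Post-shelter share = t/12: 3/12 = 25% and 6/12 = 50%.
- Pre-shelter share = (12 - t - s)/12. At 3 months this is 8.5/12 = 71% down to 7/12 = 58%. At 6 months it is 5.5/12 = 46% down to 4/12 = 33%.
- Overlap of the two follow-up windows = 12 - 3 = 9 of 12 months (75%).
- The qualifying 3 months before entry lie wholly inside a window if t + s + 3 ≤ 12, that is s ≤ 6 at the 3-month visit and s ≤ 3 at the 6-month visit. For stays up to 3 months they are counted again at both.

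To show the dilution, take the 30 items and assume that post-shelter acts are endorsed with probability 0.30 (control) and 0.20 (SHE). Let q be the assumed probability that an item is already endorsed from pre-shelter time. The difference in mean score is 30 × (0.30 - 0.20) × (1 - q): 3.0, 2.1, 1.5 and 0.9 acts at q = 0, 0.3, 0.5 and 0.7.

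Baseline adjustment recovers part of this loss. Simulations give no firm size. All inputs other than the 30 items were assumed: log-normal woman and item rates; a 1-month stay; median item rates of 0.05-0.4 per month; post/pre-shelter ratios of 0.2-0.8; SHE rate ratios of 0.5 and 0.7; and varying spread between women in post-shelter change. Relative to 3-month windows, the 12-month window kept 11-77% of the adjusted effect at 3 months and 23-96% at 6 months. The correlation between follow-ups was 0.94-0.97 with 12-month windows, against roughly 0.6-0.97 with separate 3-month windows.

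**Step 3. Reading B: twelve months at baseline, since-last-assessment at follow-up**

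Both arms share the same windows, so the between-arm contrast is not distorted. The pre-post change is. I take the score as the number of items endorsed at all, and assume a constant rate r per item per month with no true change. The chance of endorsement is 1 - exp(-12r) at baseline and 1 - exp(-3r) at follow-up. The apparent fall is 1 - (1 - exp(-3r))/(1 - exp(-12r)).

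| r per month | 12 months | 3 months | Apparent fall |
|---|---|---|---|
| 0.05 | 0.451 | 0.139 | 69% |
| 0.1 | 0.699 | 0.259 | 63% |
| 0.2 | 0.909 | 0.451 | 50% |
| 0.4 | 0.992 | 0.699 | 30% |
| 1.0 | 1.000 | 0.950 | 5% |

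For weekly acts the fall is about 0%.

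**Step 4. Since-last-assessment as the scoring window**

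A woman who misses the 3-month visit would have about 6 post-shelter months in her 6-month score. The ratio (1 - exp(-6r))/(1 - exp(-3r)) is 1.86, 1.74, 1.55 and 1.30 at r = 0.05, 0.1, 0.2 and 0.4. Her count would be that much higher than that of an otherwise identical woman seen at 3 months.

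**The case against.** The twelve-month sentence sits among the scale's subscales, item count and response options and carries a citation. It can fairly be read as describing the published instrument. The safety sentence is the only one that says how this study will use the CAS at follow-up. On that reading the two follow-up windows together cover the 6 post-shelter months, and what remains is an unstated baseline window and two sentences to reconcile. This stands in part, and it limits the point. It does not settle the matter, because no place says that the published format was changed, and the analysis section takes up neither look-back.

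A reader might infer more than the documents support:

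- That a twelve-month window will in fact be used at follow-up and will contaminate the outcome. The documents show an inconsistency, not a wrong window in use.
- That the outcome has no window at all. It has a nominal one, the 6 months after shelter; what is not fixed is the recall period that would deliver it. The SAP's silence is an omission, not a third conflicting statement.
- That the between-arm comparison is invalid. Under Reading B it is not; under Reading A it is diluted.
- That the dilution or the inflated correlation has a known size. The simulated ranges are wide and rest on assumed rates. If post-shelter abuse varies strongly between women, the loss at 6 months and the rise in correlation can be small.

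It can also be said that reconciling the sentences is enough and that 90 days is a preference. That is fair as to the exact number. Equal length at every visit is not merely a preference, because the pre-post change depends on it.

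**Conclusion.** The concern holds as an unreconciled recall period, and it is minor. If twelve months is used throughout, no more than a quarter of the 3-month window and half of the 6-month window is post-shelter. That follows from the calendar alone; the resulting loss of effect does not, and I put no figure on it. If twelve months is used only at baseline, the between-arm contrast is sound, but the pre-post reduction is partly mechanical. The size of that artefact rests on assumed constant item rates and on scoring each item as endorsed or not: large for infrequent acts, negligible for weekly ones. Either way, only one secondary, exploratory outcome and some planning estimates are affected, in a study whose primary goal is feasibility and acceptability.

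**What to change.** Reconcile the CAS paragraph in Measures, the CAS sentence under Protection against risk, the scoring rule in Data Analysis, and the SAP. State one recall period of equal length for the CAS outcome score at all visits. About 90 days fits the rest of the plan: the 90 days before shelter entry at baseline, consistent with the TLFB anchor, and the past 90 days at the 3- and 6-month visits. Ninety days is also the window length for service use, although that measure has no stated pre-shelter anchor. Keep the since-last-assessment question for safety monitoring, outside the outcome score.

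The work is to reword the scale's stem and frequency anchors in the software, add one monitoring question, and amend the four places above. The costs are a departure from the published twelve-month format, less comparability with outside data, and months 0-3 unscored for women who miss the 3-month visit. The monitoring question would still record whether abuse occurred in that gap.

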The computerized intervention will begin with a baseline **assessment** of substance use. Participants will then receive immediate “profiles” (**personalized feedback**) based on their answers to assessments. A substance use profile will summarize their typical pattern of substance use, their substance use risk level, the known health and societal consequences associated with their level of substance use, and the negative consequences they identified as resulting from substance use. Next there will be an **education** component that will deliver facts about the woman’s substance use, and associated risks for the woman, including partner substance use; the **bidirectional relationship** between substance use and IPV; and risks of untreated substance use such as increased risk of IPV.

A limitation of some clinical trials of MI-based interventions for substance use and most clinical trials of behavioral interventions for IPV is the imbalance in intensity of sessions between the experimental intervention and control group, which makes it difficult to determine if intervention differences are attributable to differences in attention between the conditions or to the “active ingredients” of the intervention. Because the proposed non-MI control condition will be matched for duration, level of interactivity, and mode of delivery and has been shown to be a credible control condition, it will provide a reasonable test of the effect of the SHE Program. Furthermore, our control condition will have no overlapping content with the SHE Program. Finally, since both conditions will be computer-based of similar duration, the blinding of research staff to experimental condition will be facilitated.

There are no standard or universal procedures in place for screening and brief interventions for women with IPV and substance use issues. Like most battered women shelters, WCRI does not conduct any formal or systematic substance use-related assessments or interventions for their residents, besides appropriate referrals for substance use treatment, if requested, or if needed (i.e., resident discloses difficulties or is found to be using alcohol or drug during her shelter stay). All participants who consent for the RCT study (and open trial) will receive a list of appropriate substance use treatment referrals and community resources (e.g., NA, AA) and a brochure on alcohol and drug risks.

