### **Control condition**

Control group participants will complete the same assessment measures. After randomization, participants in the control condition will receive a 50-minute session and a 15-minute booster session within three weeks after the initial session on the Tablet PC, which will comprise of the viewing of popular entertainers/shows videos. See above for description of the control condition. This condition will control for time spent on the computer-based intervention, maintain blinding of research assistants, and mimic the interactivity of the computer-based intervention condition. The control condition will be conducted in a private space at the shelter during participants' shelter stay.

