**Table 1: Schedule of Assessments:**

Measure	Intake	Post intervention and booster	3-months after shelter discharge	6 months after shelter discharge
Demographics	X			
Timeline Followback	X		X	X
Hair Sampling Testing			X	X
Breath Alcohol Testing			X	X
Urine Drug Screening			X	X
The Composite Abuse Scale	X		X	X
Safety Behavior Checklist	X		X	X
Treatment Services Review	X		X	X
Client Satisfaction Questionnaire		X		
Satisfaction with CIAS Software Scale		X		
Readiness Ruler	X		X	X

Confidence Ruler	X		X	X
Cyber Stalking Scale	X		X	X

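### Read literally, the phone follow-up rule has the research assistant give a SHE-only measure, which would reveal the arm to a role the protocol aims to keep blinded

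*Protocol*

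**What the plan says.** Four parts of the protocol bear on this.

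- **Blinding.** The Control condition section says the matched control will, among other things, "maintain blinding of research assistants". The control rationale under Study Procedure is softer: because both conditions are computer-based and of similar length, "the blinding of research staff to experimental condition will be facilitated".
- **Follow-up measures.** The Measures section leads in with "The following measures will be administered to both groups of women at baseline and at 3- and 6- months after leaving the shelter". Later in the same section comes an item for one arm only: "Women who participated in the SHE intervention will complete a computer-based measure at the 3- and 6-month follow-up assessment". It rates how far the woman met the goals on her personalized plan.
- **Phone follow-up.** The next paragraph covers women who cannot attend in person. It describes such a session as "the research assistant administering all the follow up assessments listed above via a phone session". The only carve-out from that rule is worded "with the exception of breathalyzer, urine, and hair sample testing".
- **Schedule.** The table headed "Table 1: Schedule of Assessments" has no row for the SHE-only measure.

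The SAP does not mention assessor blinding, mode of follow-up or this measure.

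**The concern.** The protocol's protection of blinding rests on the tablet: both arms have sessions of matched length and format on the same device. At an in-person follow-up, a SHE participant can complete the extra measure on the tablet without the assistant asking the questions. A phone session removes that separation, because the assistant asks everything.

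The TLFB yields the primary substance-use outcome, and the TSR and CAS yield the secondary outcomes. All are self-reported. Phone visits also lack the hair and urine tests that the protocol uses to corroborate reported drug use. If the assistant knows the arm, the way questions are put or answers recorded could differ between arms, with nothing objective at that visit to check against.

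At stake are the between-arm effect sizes that the Data Analysis section plans at each assessment, and their use as preliminary data for a larger, fully powered trial.

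**Working it through.** No arithmetic applies, so the passages are set side by side.

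1. **Does the phone rule cover the SHE-only measure?** The rule reaches all follow-up assessments listed above it. The SHE-only measure is in the paragraph directly above. The exceptions are the breath, urine and hair tests and nothing else. On the words, it is covered.
2. **Does the label computer-based take it out?** No. Measures also describes the TLFB as computer-based and says most measures are completed on the tablet. The phone rule exists to turn such measures into assistant-administered ones, so the label cannot mark an exemption.
3. **Does the measure reveal the arm?** Yes. It rates goals on a personalized plan, and Study Procedure describes that plan as part of the SHE sessions. Study Procedure also says the control shares no content with SHE, so a control woman has no such plan to rate. To know whether to ask the item, the assistant must know the arm. Asking it identifies SHE; omitting it identifies control.
4. **Same-call route.** The assistant who asks it also administers the TLFB, TSR and CAS on that call. The measure is described last in the text, but no order of administration is set. If the arm is known before those three are finished, they are not collected blind.
5. **Carry-over route.** Even if the measure comes last at a 3-month call, the assistant then knows the arm at 6 months if the same assistant does that assessment. An in-person 6-month visit may be touched too, since Measures adds "The TLFB will be done in person as well". That sentence does not say who administers the TLFB or which version is analysed, so this extension is only a possibility.
6. **Does any section close either route?** None assigns a different assessor, drops the item from calls, or places it after the outcome measures.
7. **How many women?** The documents plan 60 randomized women, expect about 41 with complete data, and cite 82% retention at 6 months in earlier work. None of these is split by mode of follow-up. Any count would only restate an assumed phone share, so none is given.

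**The case against.** The best counter-argument is that the conflict depends on one of two readings. The lead-in describes measures given to both groups, which a SHE-only item is not. Table 1 omits the item, and its follow-up columns hold only both-arm measures, including the three tests that the phone rule excepts. If the rule means that scheduled set, no conflict arises. This stands as a plausible account of what the authors meant. It does not settle the matter, because the text schedules the item at both follow-ups and does not exempt it, and staff following the words would ask it.

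Second, the blinding statements are aims attached to the matched session format. A reader might infer that the protocol promises blinded follow-up assessors and then breaks the promise. The documents do not support that: no section expressly says that follow-up assessors are blinded. What remains is that the Control condition section names research assistants, the role that runs the calls.

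Third, the setting limits the weight. Phone is a fallback, and the Retention section says Rhode Island residents rarely move out of state, though that may not hold for every recruiting shelter. Feasibility and acceptability are the primary goal, between-arm tests are exploratory, and the SAP states no null hypothesis. All of this stands, and it is why the point is a modest one.

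**Conclusion.** The point holds as a conflict on a literal reading. The phone rule, as worded, has the research assistant give an arm-revealing measure, which sits against the aim of keeping research assistants blinded. It affects the same call, and possibly the 6-month assessment if the same assistant returns.

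A reader might go further and infer that unblinding will occur, or that the substance-use comparison is biased. Neither is shown. The documents give no number of phone visits and no basis for a size of bias, and the authors may not have meant the rule to reach this item.

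The consequence is limited to women followed up by phone, and to exploratory comparisons in a pilot. It is still worth correcting before those comparisons are used to plan a larger trial, because the correction is small.

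**What to change.** **Preferred.** In the phone follow-up paragraph of Measures, add the SHE-only goal measure to the exceptions from administration by the assistant. This one clause closes both the same-call and the carry-over route.

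**Alternative, if goal data by phone are wanted.** Leave the measure out of 3-month calls. At 6-month calls, have the software bring it up only after the TLFB, TSR and CAS have been entered, so that the assistant does not need to know the arm beforehand. Asking it last at both visits would not be enough, because it leaves the carry-over from 3 to 6 months.

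**In either case.** Add the measure to Table 1, marked as SHE only, with how and when it is given. Record the mode of each follow-up. Report the number of phone visits by arm beside the between-arm estimates.

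**Cost.** One clause, one table row, one data field and one reported count. Goal-attainment data are lost for SHE women at each phone follow-up where the measure is left out. The change does not remove other ways in which staff might learn the arm, such as seeing a woman's Safety Plan print-out, nor any effect on her answers of knowing which session she had.
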